### **9.1.2. Other Safety Topics of Interest**

The following summaries of TEAEs associated with safety topics of interest will include incidence of TEAEs, treatment-related TEAEs, and serious TEAEs by PT. A listing of AEs meeting each safety topic of interest will also be generated. All Sponsor-defined terms will be identified prior to database lock and will be included in the CSR.

- Hypotension-associated TEAEs comprised of Sponsor-defined terms.
- Hepatic-associated TEAEs comprised of terms in the Hepatic Disorders Standardised MedDRA Query (SMQ), excluding the following sub-SMQs: alcohol related, congenital, familial, neonatal, and genetic disorders of the liver; liver infections; and pregnancy-related hepatic disorders.
- Fluid retention-associated TEAEs comprised of terms in the haemodynamic oedema, effusions, and fluid overload SMQ.
- Anemia-associated TEAEs comprised of Sponsor-defined terms.
- Hyperkalemia-associated TEAEs comprised of PTs “Hyperkalemia,” “Hyperkalaemia,” and “Blood potassium increased.”

## **9.2. Extent of Sparsentan Exposure and Compliance**

The following extent of exposure parameters will be summarized both continuously using descriptive statistics and categorically using counts and percentages separately for Sparsentan:

- Duration of treatment (weeks)
- Duration of treatment with reduced dose (weeks)
- Duration of treatment with target dose (weeks)
- Total duration of study medication interruptions (days)

Duration of treatment (weeks) will be calculated as follows:

- Duration of treatment =  $(\text{Date of last dose of study medication on or prior to the next scheduled visit} - \text{Date of first dose of study medication} + 1) / 7$

Duration of treatment with reduced dose and duration of treatment with target dose will be calculated similarly. For patients who have no dose reductions during the study, the duration of treatment with reduced dose will be set to 0 weeks and the duration on treatment and duration on treatment with reduced dose will be equal.

The duration of each incidence of study medication interruption will be calculated as follows:

- Duration of study medication interruption =  $(\text{Date of restart of study medication} - \text{Date of temporary discontinuation})$

The total duration of study medication interruptions is the sum of duration of study medication interruption over each incidence of interruption that occurred during the study. For patients with no study medication interruption during the study, the total duration is considered 0 days.

A summary of patients who had dose reductions will be summarized by frequency count and percentages.

Patient's compliance rate (%) with study medication during the treatment period will be calculated as follows at the final analysis:

- $100 \times ([\text{Total number of capsules dispensed} - \text{Total number of capsules returned}] / [\text{Expected number of capsules to be taken based on the patient's titration schedule}])$

Compliance rates will be summarized both continuously using descriptive statistics and categorically using counts and percentages by treatment group and overall.

Compliance will also be derived from the dose log to supplement the assessment using drug dispensation and return. Compliance based on the dose log for each patient will be determined as follows:

- Total number of capsules taken = sum over all actual dose intervals, where an actual dose interval is defined as any dose log record where actual dose > 0 capsules and derived as number of days  $\times$  number of capsules
- Total number of capsules missed = sum over all missed dose intervals defined as any record where dose = 0 capsules and eCRF indicates missed dose; derived as number of days  $\times$  number of expected capsules
- Total number of capsules taken over prescribed dose = sum of all dose intervals where dose log indicates overdose and derived as number of days  $\times$  number of capsules
- Dose log compliance =  $100 \times ([\text{Total number of capsules taken}] / [\text{Total number of capsules taken} + \text{Total number of capsules missed} - \text{Total number of capsules taken over prescribed dose}])$

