## 4. STUDY DESIGN

### 4.1. Summary of Study Design

This is a 28-week, open-label, multicenter, single-group, Phase 2 exploratory study to determine the safety and effect of sparsentan in participants with IgAN who are at risk of disease progression despite being on both stable renin-angiotensin-aldosterone system inhibitor (RAASi) and SGLT2 inhibitor treatment for at least 12 weeks prior to study entry.

Approximately 60 participants aged  $\geq 18$  years will be enrolled into this study.

[figure not shown]
Participants who provide written informed consent will be assessed for eligibility and will undergo baseline evaluations including clinical laboratory tests. Per the eligibility criteria, all participants are required to be on a stable dose(s) of angiotensin converting enzyme inhibitor (ACEI) and/or angiotensin receptor blocker (ARB) and on a stable dose of a SGLT2 inhibitor at screening and will continue their stable treatments through the screening period. Eligible participants entering the study will remain on the stable dose of the SGLT2 inhibitor for the duration of the study, however, they will discontinue ACEI and/or ARB therapy before the Day 1 visit. The final dose of an ACEI and/or ARB should be taken on the day before the Day 1 visit. Baseline evaluations will be taken on Day 1 prior to administration of the first dose of the study medication (sparsentan).

Study medication will be administered daily for a treatment period of 24 weeks with study visits conducted at weeks 2-, 4-, 12-, and 24- following Day 1. Following the 24-week treatment period, study medication will be discontinued for 4 weeks. At this time, the Investigator should resume standard of care treatment, including RAASi treatment. Participants will return to the site for a visit at Week 28 for the safety follow-up visit.

UA/C and UP/C will be determined using first morning void (FMV) samples and will be calculated as the average of 2 FMV samples collected within 3 days prior to each visit. If 1 of the samples is missing, UA/C and UP/C from the single sample will be used.

The overall study design is summarized in Figure 1 (below). For individual participants, the total duration of participation from the screening visit to the safety follow-up visit (Week 28) will be a maximum 34 weeks.

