## **4.2. Definition of Study Medication**

Study interventions are all pre-specified, investigational, and non-investigational medicinal products, medical devices, and other interventions (eg, surgical, and behavioral) intended to be administered to the study participants during the study conduct.

At the Week 1 the starting dose will be 1 tablet ( $1 \times 200$  mg) taken prior to the morning meal.

Starting at week 3 the dose will be titrated to 1 tablet ( $1 \times 400$  mg) taken prior to the morning meal, if tolerated and determined safe by the Investigator.

Patients can continue initial dose without titration or have dose reductions back to the initial dose (reduced dose) after dose titration based on tolerability as described in the protocol.

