### 7.3. Protocol Deviations

Protocol deviations for missed visits, missed assessments, out-of-window visits or assessments, and violations of inclusion/exclusion criteria (where possible) will be determined based on available data. The clinical research associates will collect all other protocol deviations. Protocol deviations will be classified as critical, important, major, or minor as follows:

- Critical: A deviation from Protocol-related procedures that threatens integrity of data, adversely affects subjects and/or could invalidate acceptability of a project (or part of it). Such deviations require immediate action. This classification will only be used for a confirmed Serious Breach or a serious quality issue. Both circumstances will involve Quality Assurance.
- Important: A subset of protocol deviations that may significantly impact the completeness, accuracy and/or reliability of key study data or that may significantly affect a subject's rights, safety or well-being.

- Major: A deviation from Protocol-related procedures that could affect integrity of the data or adversely affect subjects. Such deviations require timely action.
- Minor: A deviation from accepted procedures that will not adversely affect subjects or data integrity but should be dealt with appropriately.

Protocol deviations that could potentially affect the efficacy or safety conclusions of the study will be identified, and the assessment of determination of evaluable patients for the PPAS will be performed and approved by the Study Statistician, Medical Monitor and Clinical Study Manager prior to database lock.

Evaluability of patients will be based on the following:

- Compliance of study entry criteria (inclusion and exclusion)
- Adequate study medication exposure (no extended dosing interruptions)
- Adequate treatment compliance based on prescribed dose level (within 80% to 120%)
- No prohibited concomitant medications or therapies during the study
- No other major protocol deviations that may affect efficacy or safety conclusions, including the following:
  - Non-withdrawal although at least 1 withdrawal criterion was met.
  - Extensive visit window violations
  - Extensive missing visits
  - Nonadherence to study procedures
  - Inadequate handling of study medication

Critical/Important/Major protocol deviations will be summarized by deviation category and presented in a by-patient data listing.

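### The SAP's dose-log compliance formula, followed literally, subtracts all capsules taken on overdose days rather than only the excess, which inflates the percentage whenever an overdose is logged

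*SAP*

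**What the plan says.** SAP 9.2 gives two compliance measures. The first is capsules dispensed minus capsules returned, divided by the number expected under the participant's titration schedule. The second comes from the dose log and is introduced as a supplement to the first. It is built from three counts:

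- **Taken:** "an actual dose interval is defined as any dose log record where actual dose > 0 capsules and derived as number of days", multiplied by the number of capsules. Overdose days are therefore counted in full.
- **Missed:** days multiplied by the "number of expected capsules".
- **Over:** labelled "Total number of capsules taken over prescribed dose" and derived as the "sum of all dose intervals where dose log indicates overdose and derived as number of days", multiplied by the number of capsules.

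Dose-log compliance is 100 × taken / (taken + missed − over).

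SAP 7.3 lists the criteria for evaluability in the Per Protocol Analysis Set (PPAS). One of them is "Adequate treatment compliance based on prescribed dose level (within 80% to 120" per cent. It does not say which of the two measures is meant.

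**The concern.** The label of the third count and its derivation do not match. The label describes an excess. The derivation is the same product used for capsules taken, and nothing in it removes the prescribed amount. Only the line for missed capsules refers to the expected number.

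The denominator should equal the number prescribed, as it does in the dispensed/returned measure. It does so only if the third count is the excess. If it is everything taken on overdose days, the denominator is too small and the percentage too high.

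What is at stake is the supplementary compliance summary and, if this measure is the one applied in SAP 7.3, membership of the PPAS. SAP 8.2.4 uses that set for sensitivity analyses of the primary and secondary efficacy endpoints.

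**Working it through.** The SAP gives no worked compliance figure, so there is none to reproduce. I applied the formula directly.

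**Inputs from the documents**

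- Length: "Study medication will be administered daily for a treatment period of 24 weeks" (SAP 4.1), so D = 24 × 7 = 168 days.
- Prescribed units: "the starting dose will be 1 tablet" and later "the dose will be titrated to 1 tablet" (SAP 4.2). That is one unit per day at either strength, or 168 in all. SAP 9.2 counts capsules where SAP 4.2 describes tablets; I treat them as the same unit.

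**Assumptions, not in the documents**

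- k units are taken on an overdose day, with k = 2 as the main case and k = 3 as a variation.
- d is the number of overdose days and m the number of missed days.

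**Formulas**

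- Taken: T = (D − m − d) + kd. Missed: m.
- As written: over = kd, so the denominator is T + m − kd = D − d. It is one unit short of the prescribed number for every overdose day.
- Excess only: over = (k − 1)d, so the denominator is T + m − (k − 1)d = D, the prescribed number.

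**Results for k = 2, m = 0**

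| d | As written | Excess only |
|---|---|---|
| 5 | 173/163 = 106.1% | 173/168 = 103.0% |
| 10 | 178/158 = 112.7% | 178/168 = 106.0% |
| 15 | 183/153 = 119.6% | 183/168 = 108.9% |
| 16 | 184/152 = 121.1% | 184/168 = 109.5% |
| 33 | 201/135 = 148.9% | 201/168 = 119.6% |
| 34 | 202/134 = 150.7% | 202/168 = 120.2% |

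If every tablet not returned was taken, the dispensed/returned measure equals the right-hand column. The two SAP measures then disagree on the same intake.

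**Upper limit.** For 16 to 33 overdose days the written formula exceeds 120% while the true ratio does not. With k = 3 the range is 11 to 16 days; at d = 11 the figures are 190/157 = 121.0% and 190/168 = 113.1%.

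**Lower limit.** With m = 40 and k = 2, T = 128 + d. At d = 4 the written formula gives 132/164 = 80.5% against 132/168 = 78.6%. At d = 6 it gives 134/162 = 82.7% against 134/168 = 79.8%. At d = 7 the true ratio reaches 80% as well (135/168 = 80.4%). So 4 to 6 overdose days carry the participant to 80% wrongly.

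**Limiting case.** If every day is an overdose day (d = 168, k = 2, m = 0), taken and over are both 336. The written denominator is zero and compliance is undefined. The excess-only form gives 336/168 = 200%.

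**The case against.** The strongest reply is that the label already says what is meant. Subtracting the term makes sense only for an excess, and a programmer may well code it that way. If the dose log held the extra capsules as separate overdose records, the product as written would pick up only the excess and the denominator would be right. The label argument stands in part: it shows the likely intent. It does not remove the problem, because someone following the label and someone following the derivation would get different numbers. The separate-record reading has no support in the documents; the SAP does not describe the log that way.

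A reader might infer that the formula will wrongly remove participants from the PPAS. The documents do not support that. SAP 9.2 makes the dose-log figure a supplement to a dispensed/returned rate that is free of this fault, and SAP 7.3 does not name the measure tested. SAP 7.3 also has evaluability assessed and approved by the study statistician, the medical monitor and the clinical study manager before database lock, so automatic exclusion on this percentage is not shown. Crossing 120% wrongly takes 16 assumed double-dose days with none missed, which is 16/168 = 9.5% of days. Someone with that record might fail another criterion in any case. These limits all stand, and they set the size of the point.

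**Conclusion.** The derivation contradicts its own label and gives a wrong percentage if followed. Dose-log compliance is then too high for any participant with a logged overdose. At double dose with none missed, the excess is 3.1 percentage points for 5 overdose days (106.1 − 103.0) and 6.7 points for 10 (112.7 − 106.0). It is zero when no overdose is logged.

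Any effect on the PPAS is conditional on the dose-log measure being the one held against 80% to 120%. If it is, the error can run either way: 16 to 33 double-dose days with none missed would wrongly exceed 120%, and 4 to 6 with 40 days missed would wrongly reach 80%. These ranges rest on the assumed two tablets per overdose day and a full 168 days.

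The primary analysis uses the Full Analysis Set (SAP 5.1), and so do the safety analyses (SAP 6.3.1). Neither depends on the 80% to 120% criterion. Protocol 9.1 sets no efficacy hypothesis. Severity is minor.

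**What to change.** In SAP 9.2, derive the third count as the sum over overdose intervals of days × (capsules taken − capsules prescribed). The denominator then equals the prescribed number, and the dose-log measure agrees with the dispensed/returned rate whenever the underlying intake agrees.

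In SAP 7.3, state which compliance measure the 80% to 120% criterion uses.

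The cost is one line in SAP 9.2 and a few words in SAP 7.3, before database lock. The formula needs no new kind of input, because the line for missed capsules already relies on the expected number.

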### 9.3. Extent of SGLT2 Inhibitor Exposure

The following extent of exposure parameters will be summarized both continuously using descriptive statistics and categorically using counts and percentages separately for Sparsentan:

- Type of SGLT2 inhibitor (ie, Dapagliflozin)
- Percentage of MLD at Baseline (Overall and by type of SGLT2 inhibitor)
- Duration of total treatment (weeks)
- Duration of treatment concomitantly with Sparsentan (weeks)
- Duration of treatment with reduced dose (from Baseline) concomitantly with Sparsentan (weeks), if any dose reductions occur
- Total duration of study medication interruptions (days)

The number and percentage of patients on each recorded SGLT2 Inhibitor will be summarized.

Percentage of MLD at Baseline will be calculated as follows:

- Percentage of MLD at Baseline =  $100 \times (\text{Total daily dose received}) / (\text{Total maximum labeled daily dose for the given medication})$ .

Percentage of MLD at Baseline will be summarized continuously and with counts and percentages for the following buckets:

- 0% to <25%
- 25% to <50%
- 50% to <75%
- 75% to 100%
- >100%

Duration of total treatment (weeks) will be calculated as follows:

- Duration of treatment =  $(\text{Date of last dose of study medication or date of completion/early discontinuation if patient is still ongoing on SGLT2 Inhibitor at end of study} - \text{Date of first dose of SGLT2 Inhibitor} + 1) / 7$

Duration of treatment concomitantly with Sparsentan (weeks) will be calculated as follows:

- Duration of treatment =  $(\text{Date of last dose of study medication on the same day as a dose of Sparsentan} - \text{Date of first dose of study medication on or after the first dose of Sparsentan} + 1) / 7$

Duration of treatment with reduced dose will be calculated similarly. For patients who have no dose reductions during the study, the duration of treatment with reduced dose will be set to 0 weeks and the duration on treatment concomitantly with Sparsentan and duration on treatment with reduced dose concomitantly with Sparsentan will be equal.

The duration of each incidence of SGLT2 inhibitor interruption will be calculated as follows:

- Duration of SGLT2 inhibitor interruption = (Date of restart of SGLT2 inhibitor – Date of temporary discontinuation)

The total duration of SGLT2 inhibitor interruptions is the sum of duration of SGLT2 inhibitor interruption over each incidence of interruption that occurred during the study. For patients without SGLT2 inhibitor interruption during the study, the total duration is considered 0 days.

A summary of patients who had dose reductions will be summarized by frequency count and percentages.

#### **9.4. Prior and New Concomitant Medications and Procedures**

Prior and concomitant medications and procedures will be collected from 3 months prior to Screening through the patient's final study visit. In addition, a comprehensive history of medications previously used for treatment of IgAN, including systemic corticosteroids or other systemic immunotherapeutic agents, will be collected. For medications, verbatim terms on eCRFs will be mapped to Anatomical Therapeutic Chemical (ATC) class and preferred name using the World Health Organization (WHO) Drug Dictionary Enhanced. For procedures, verbatim terms will be mapped to PTs and SOC using MedDRA.

Pretreatment medications are those medications with start and stop dates prior to the initial dose of study medication. Prior concomitant medications are those medications started prior to and continued after the initial dose of study medication. New concomitant medications are those medications that were started on or after the initial dose of study medication. If it cannot be determined whether the medication was a new concomitant medication due to a partial start or stop date or if the medication is taken on the same date as the initial dose of study medication, then it will be counted as a new concomitant medication.

Similarly, prior procedures are those procedures with a start date prior to the initial dose of study medication. Concomitant procedures are those procedures that were started after the initial dose of study medication.

Pretreatment medications will be listed only.

Prior and new concomitant medications will be summarized separately by WHO ATC level 2, WHO ATC level 4, and preferred name. These summaries will present the number and percentage of patients using each medication. Patients may have more than 1 medication per ATC level and preferred name. At each level of patient summarization, a patient is counted once if he/she reported 1 or more medications at that level. Each summary will be ordered by descending order of incidence of ATC level and preferred name within each ATC level.

Prior and concomitant procedures will be summarized for each treatment group by SOC and PT. Each summary will be ordered by descending order of incidence of SOC and PT within each SOC.

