Brief Summary: This is a 28-week, open-label, multicenter, single-group Phase 2 exploratory study to determine the safety and effect of sparsentan in participants with IgAN who are at risk of disease progression to KF despite being on both stable RAASi and SGLT2 inhibitor treatment for at least 12 weeks prior to study entry.

Health Measurement/Outcome: The purpose of this study is to evaluate safety and effect of sparsentan in combination with SGLT2 inhibitors in adult participants with IgAN.

Study Intervention and Intervention Form: Sparsentan tablets

Condition/Disease: IgAN

Study Duration: The duration of the study for a participant will be up to 34 weeks.

Treatment Duration: The study design included a screening period of up to 6 weeks, treatment period of 24 weeks, and a follow-up period of 4 weeks.

Visit Frequency: Site visits will be conducted for screening, at Day 1 (baseline), and at weeks 2, 4, 12, and 24 following Day 1. Following the 24-week treatment period, study intervention will be discontinued for 4 weeks. At this time, the Investigator should resume standard of care treatment, including RAAS inhibitor treatment. Participants will return to the site for a visit at Week 28 for the safety follow-up visit.

Number of Participants:

Approximately 60 participants aged ≥ 18 years will be enrolled into this study.

Note: Enrolled means participants', or their legally acceptable representatives', agreement to participate in a clinical study following completion of the informed consent. Potential participants who are screened for the purpose of determining eligibility for the study, but do not participate in the study, are not considered enrolled, unless otherwise specified by the protocol.

Study Arms and Duration:

This study includes 3 periods: a screening period (up to 42 days), a treatment period (24 weeks) and a follow-up period (4 weeks).

All participants will be on stable doses of standard of care ACEI and/or ARB and an SGLT2 inhibitor at study entry, with prohibited concomitant medications discontinued before the baseline (Day 1) visit. The full daily dose of study intervention (sparsentan) is preferred to be taken prior to the morning meal, with the exception of the day of a study visit. Allowed doses of sparsentan during the treatment period are 200 mg and 400 mg. The goal is to titrate from the initial dose of 200 mg (Day 1) to the target dose of 400 mg at Week 2.

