10.6. Appendix 6: Concomitant Medication Considerations

A. While Taking Study Intervention (Starting from Day 1 to Week 24)

1. Prohibited Medications While Taking Study Intervention (Starting from Day 1 to Week 24)
 - Inhibitors of the RAAS.
 - Examples include (not all inclusive) the following: ACEIs, aldosterone blockers, ARBs, ERAs and aliskiren.
 - Inhibitors of the endothelin system (eg, bosentan, macitentan, and ambrisentan).
 - Potassium sparing diuretics (eg, amiloride and triamterene).
 - Thiazolidinediones should be avoided completely. Other anti-diabetic drugs (eg, metformin and glyburide) should be used in accordance with their guidelines for use in patients with impaired kidney function.
 - Digoxin, amiodarone, or any other antiarrhythmic medications that may put the patient at higher risk due to the underlying disease.
 - St. John's Wort or other hypericum-derived products.
 - Strong Cytochrome P450 3A (CYP3A) inhibitors. For a detailed list of these medications, see the P450 Drug Interaction table at:
<http://medicine.iupui.edu/clinpharm/ddis/maintable>.
NOTE: The Sponsor recognizes that, in some cases, concomitant use of these medications may be medically necessary (eg, azole antifungals for severe mycotic infections), and alternatives are either unavailable or inappropriate from a medical and safety perspective. In these cases, limited systemic exposure may be warranted; however, systemic use of strong CYP3A4 inhibitors should be avoided. In addition, a reduction in dose or temporary cessation of study intervention and more intensive patient monitoring is recommended.
- The following medications are prohibited for 7 days prior to study visits and should be used with caution at other times during the study. Investigators must review each participant case individually and use clinical judgment.
 - Sulfamethoxazole/trimethoprim (eg, Bactrim™ and Septra®), cimetidine, pyrimethamine, cetirizine, cobicistat, probenecid, vandetanib, dolutegravir, ranolazine, dronedarone, ritonavir, and telaprevir cannot be used within at least 7 days prior to any visit at which eGFR is assessed.
 - Fibrates.
2. Medications to be Used with Caution While Taking Study Intervention (Starting from Day 1 to Week 24)

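### SAP 9.4 sets no end date for new concomitant medications, so post-treatment starts, including resumed ACEI/ARB, are pooled with on-treatment starts; its same-date rule also contradicts its own definition of prior concomitant

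*SAP*

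**What the plan says.** SAP 9.4 first sets the collection period: "Prior and concomitant medications and procedures will be collected from 3 months prior to Screening through the patient's final study visit". SAP Table 1 gives target days of 169 for Week 24 and 197 for Week 28, so the medication record extends past the planned end of dosing.

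It then defines three categories:

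- Pretreatment: started and stopped before the first sparsentan dose. These are listed only.
- Prior concomitant: "Prior concomitant medications are those medications started prior to and continued after the initial dose of study medication".
- New concomitant: "New concomitant medications are those medications that were started on or after the initial dose of study medication".

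No category covers starts after the last dose. A closing rule counts a drug as new if partial dates leave its status unclear, and also if it is "taken on the same date as the initial dose of study medication, then it will be counted as a new concomitant medication". On the tables, the section says: "These summaries will present the number and percentage of patients using each medication". A patient counts once per ATC level and once per drug name, with no split by period.

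The design fixes what will enter that table. Under Protocol 4.1 and SAP 4.1, the last ACEI/ARB dose is taken the day before Day 1, and the SGLT2 inhibitor continues throughout. Protocol Appendix 6 part A, headed "Prohibited Medications While Taking Study Intervention (Starting from Day 1 to Week 24", includes ACEIs and ARBs. After the 24-week treatment period the Protocol synopsis says: "At this time, the Investigator should resume standard of care treatment, including RAAS inhibitor treatment". Footnote g to the Schedule of Activities expects standard of care to restart but leaves the RAAS inhibitor restart to the Investigator's discretion. Appendix 6 part B, covering Weeks 24 to 28, does not list ACEI/ARB.

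**The concern.** A reader takes a table of new concomitant medications to show what was added alongside sparsentan. Here it also includes what was added after sparsentan stopped, and the design makes such additions likely in the drug class that was deliberately withdrawn at entry. A compliant participant who resumes an ACEI/ARB at Week 24 looks the same in the table as one who started an ACEI/ARB during treatment.

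Diuretics and other antihypertensives are affected too. Starts of these on treatment carry safety information, because the protocol uses diuretics for fluid retention and hyperkalemia and antihypertensives for blood pressure. Starts on return to standard of care do not carry that information.

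The SAP bounds time elsewhere. Treatment-emergent adverse events are confined to the treatment period (SAP 9.1), and on-treatment efficacy data end 3 days after the last dose (SAP 8.1). Section 9.4 has no equivalent bound.

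The same-date rule is a separate defect. Any daily drug continued through Day 1 is taken on the date of the first dose, so it meets both the prior concomitant definition and the rule that makes it new. Two programmers could produce different tables from the same data.

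**Working it through.** The plan states no figure on this point, so there is none to reproduce. The check applies the rules to cases and then sizes the pooling under a stated assumption.

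**Step 1. Length of the unbounded period.** From the SAP Table 1 target days: 197 − 169 = 28 days off sparsentan, during which a start still counts as new concomitant.

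**Step 2. The SAP 9.4 rules applied to five histories.**

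| History | By start date | By the literal same-date rule |
|---|---|---|
| ACEI/ARB stopped the day before Day 1 (compliant) | Pretreatment, listed only | Pretreatment, listed only |
| ACEI/ARB resumed after Week 24 (permitted) | New | New |
| ACEI/ARB first started during treatment (prohibited) | New | New |
| ACEI/ARB never stopped at Day 1 (prohibited) | Prior concomitant | New |
| Background SGLT2 inhibitor | Prior concomitant | New |

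Rows 2 and 3 receive the same label under either reading. Rows 4 and 5 change label with the reading. The pooling of permitted and prohibited use therefore concerns ACEI/ARB started on treatment; by start date, an ACEI/ARB that was never stopped goes to the other table.

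**Step 3. Size of the pooling.** Planned N = 60 (SAP 4.3.1). Let k be the number who newly start an ACEI/ARB on treatment and r the proportion who restart after the last dose. The documents give neither. Assumptions: k = 0 to 12, r = 50% to 100%, restart independent of on-treatment use, and ACEI and ARB read together as one class. Each patient counts once, so the expected number displayed is k + (60 − k) × r.

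Example: k = 3 and r = 90% gives 3 + 57 × 0.9 = 54.3, and 54.3/60 = 90.5%. The on-treatment figure is 3/60 = 5%.

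| Restart r | k = 0 (true 0%) | k = 3 (true 5%) | k = 6 (true 10%) | k = 12 (true 20%) |
|---|---|---|---|---|
| 50% | 50.0% | 52.5% | 55.0% | 60.0% |
| 75% | 75.0% | 76.3% | 77.5% | 80.0% |
| 90% | 90.0% | 90.5% | 91.0% | 92.0% |
| 100% | 100% | 100% | 100% | 100% |

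Reading across a row, a 20-point difference in true on-treatment starts moves the display by 10 points at r = 50%, by 2 points at r = 90% and not at all at r = 100%.

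Independence is not critical. At r = 50% and a true rate of 20%, complete overlap gives 50% and no overlap gives 50% + 20% = 70%. If nobody restarted (r = 0), the display would equal the true rate and there would be no distortion.

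**Step 4. The same-date wording.** If started was meant, the clause adds nothing, because the definition of new already covers starts on the first-dose date. If taken was meant, it contradicts the definition of prior concomitant in the same paragraph.

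**The case against.** The strongest reply is that this table is not where the plan checks prohibited use. SAP 7.3 requires no prohibited concomitant medication for inclusion in the per protocol set, with that assessment approved before database lock. Critical, important and major deviations are summarised by category and listed by patient. Appendix 6 bounds the prohibition in time, so a Week 24 restart is not a deviation and on-treatment use is. SAP 6.1 puts individual data in by-patient listings, and Protocol 6.8 collects start and end dates. All of this stands: the information is not lost. It does not repair the table, because deviation summaries do not give drug-level incidence of permitted on-treatment additions such as diuretics.

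A reader might infer that nearly every completer will show a new ACEI/ARB. The documents do not support a rate: the body text says standard of care should be resumed, while footnote g makes the RAAS inhibitor restart discretionary.

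A reader might also infer that the efficacy result is compromised. It is not: no efficacy analysis uses the SAP 9.4 categories, and the primary analysis is restricted to on-treatment data (SAP 8.1 and 8.2.1).

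Finally, the literal same-date reading would move every continuing daily drug out of the prior concomitant table, so it was probably not intended. SAP 9.3 also reports SGLT2 inhibitor exposure separately, including duration alongside sparsentan. That limits the harm; the contradiction in the text remains.

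**Conclusion.** The point holds as a minor correction to a descriptive table. Followed exactly, SAP 9.4 counts starts made after sparsentan has stopped as concomitant with it, and so overstates new RAAS inhibitor use alongside sparsentan. Under the assumed restart range of 50% to 100%, independent of on-treatment use, true on-treatment start rates of 0% to 20% would display as about 50% to 100%. The size depends wholly on the restart rate, which the documents do not give; the direction does not.

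The same-date rule contradicts the prior concomitant definition and, read literally, makes every daily background drug new, including the SGLT2 inhibitor.

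It would go too far to say that breaches of the RAAS inhibitor prohibition are hidden from the study report. Deviation reporting, per protocol review and listings still show them.

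**What to change.** Amend SAP 9.4 as follows:

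1. Split new medications at each participant's own last sparsentan dose: on-treatment starts (first dose through last dose) and post-treatment starts (after the last dose), tabulated separately. Using the individual date also handles early discontinuation. State that a RAAS inhibitor resumed at the Week 24/EOT visit on the date of the last dose counts as post-treatment; otherwise permitted restarts on that date would fall on the wrong side. This is a rule for the table only.
2. Add a row for any RAAS inhibitor use overlapping the sparsentan treatment period, whatever its start date, so that an ACEI/ARB never stopped at Day 1 is captured.
3. Flag partial start dates that cannot be placed before or after the last dose. SAP 6.6.3 sets a missing day in a later month to the first of that month, which can move a post-treatment restart to before the last dose.
4. In the same-date rule, replace taken with started.

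The body text and footnote g on RAAS inhibitor resumption should also be reconciled, so that the table's reader knows what was expected.

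The cost is small: a few sentences, one extra table and a boundary rule to program. The dates are already collected, and no efficacy analysis or sample size changes.
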